2.3.3 Patient disposition

The number of patients who were screened and screening failures will be presented. In addition, the reasons for screen failures will be provided. The number and percent of patients who completed or discontinued the IV treatment and study (including the reason for discontinuation) will be presented for each treatment group and overall.

For each protocol deviation, the number and percent of patients for whom the deviation applies will be tabulated. Protocol deviations or non-protocol deviation criteria leading to exclusion from analysis sets will be summarized.

Randomized set will be used.

2.4 Treatments (study treatment, rescue medication, concomitant therapies, compliance)

2.4.1 Study treatment / compliance

Total number of doses and total dose (in mg) for each IV study drug will be summarized by treatment group. Number and percent of patients with different number of doses will be provided. Duration of IV treatment (in days) will be summarized by treatment group. Total number of doses, total dose of Coartem as oral therapy will also be summarized by treatment group; total dose in mg for Coartem is number of tablets multiplied with strength of the tablets in mg.

Number and percent of patients with minimal doses of IV study drug (2 doses for KAE609 and 3 doses for artesunate) will be provided.

Safety set will be used.

2.4.2 Prior, concomitant and post therapies

Prior and concomitant medications will be summarized in separate tables by treatment group.

Concomitant IV rescue and other anti-malarial medications will also be summarized by treatment group and drug.

Note – If a patient is randomized to IV cipargamin regimen but receiving IV artesunate per investigator's discretion, the IV artesunate will be classified as rescue medication. IV artesunate as rescue medications will be captured in DAR CRF whereas, other antimalarials will be recorded in concomitant medications CRFs.

Prior medications are defined as drugs taken and stopped prior to the first dose of study medication. Any medication given at least once between the day of first dose of study medication and the last day of study visit will be a concomitant medication, including those which were started pre-baseline and continued into the treatment period.

Prior and concomitant medications will be coded according to the latest version of WHO Drug Reference List dictionary which employs the ATC. The number and percentage of patients taking prior and concomitant medications will be summarized for each treatment by ATC class and preferred term (PT).

Number and percentages of the patients using concomitant medications in the management of signs and symptoms of severe malaria by treatment group will be summarized. A listing will be provided. These drugs will be identified from the clinical database prior to database lock. Number and percent of patients receiving concomitant non-study drug antimalarial will be provided by treatment group (See [Table 5-11](#)).

A listing of the patients who received prohibited prior and concomitant drugs will be provided. It is anticipated that only few patients will receive prohibited prior and concomitant drugs. Separate summary table for prohibited prior and concomitant drugs may also be provided if a higher number of patients are reported to receive such medicines. Prohibited drugs will be identified from the clinical database prior to database lock.

Safety set will be used. In case of differences in the safety set and FAS, the analysis will also be repeated on FAS.

2.5 Analysis of the primary objective

2.5.1 Primary Estimand

An estimand is a precise description of the treatment effect reflecting the clinical question posed by the trial objective. It summarizes at a population-level, what the outcomes would be in the same patients under each of the treatment conditions being compared. Attributes of an estimand include the population, variable (or endpoint) and treatment of interest. It also specifies how intercurrent events are addressed and provides a population-level summary for the variable. The structured framework of estimand detailed in ICH E9 (R1) was newly adopted by the Regulatory Members of the ICH Assembly under Step 4 in Nov-2019.

The clinical question of interest is: What is the difference between IV cipargamin and IV artesunate in early reduction of asexual parasite load in patients with severe *P. falciparum* malaria who are treated with at least one dose of IV treatment?

The justification for targeting this treatment effect is that severe *P. falciparum* malaria is caused by asexual parasite burden, leading to sequestration and microvascular obstruction. Rapid reduction of *P. falciparum* asexual parasites by 12 hours should prevent patients from further deterioration, and so allow eventual recovery from the disease.

The primary estimand is described by the following attributes:

1. Population: Patients with severe *P. falciparum* malaria and who have been treated with at least one dose of IV study medication (either cipargamin or artesunate). Further details about the population are provided in Section 5 in the protocol.
2. Variable: A binary outcome indicating $\geq 90\%$ reduction in *P. falciparum* parasite at 12 hours (H12) after first IV dose as compared to baseline. A patient is considered as achieving primary endpoint if *P. falciparum* asexual parasite reading at 12 hours is either absent or with a positive value that is $\leq 10\%$ of the baseline value.
3. Treatment of interest: IV cipargamin vs IV artesunate. Further details about cipargamin and artesunate are provided in Section 6 in the protocol .
4. Intercurrent events: (1) taking IV rescue antimalarial medication prior to H12 parasite assessment, or (2) mortality prior to H12 parasite assessment. Details on how to handle the intercurrent event are provided in [Section 2.5.3](#).
5. Population level summary measure: Difference in proportion of patients with $\geq 90\%$ reduction in baseline parasite count between IV cipargamin dose regimen and IV artesunate will be evaluated within each cohort separately except Cohort 1, which will be combined with Cohort 2.

2.5.2 Statistical hypothesis, model, and method of analysis

The statistical null hypothesis is that the difference in proportion of patients with $\geq 90\%$ reduction at 12 hours between a cipargamin dose regimen and artesunate is ≤ -0.1 with the alternative hypothesis that the difference is > -0.1 .

The statistical hypothesis will be tested at the 2-sided 10% significance level without multiplicity adjustment for multiple comparison due to multiple cipargamin dose regimen. Two-sided 90% confidence intervals (CI) for the difference between each cipargamin dose regimen vs artesunate will be provided using the Wilson uncorrected method: a cipargamin dose regimen is said to be non-inferior to artesunate if the lower limit of CI is > -0.1 .

The hypothesis will be tested for each Cohort separately except Cohort 1, which will be combined with Cohort 2.

Data from patients in Cohorts 1 and 2 will be pooled together to allow evaluation of non-inferiority to artesunate since both cohorts include patients aged ≥ 12 years although patients in Cohort 1 are milder in clinical condition compared to patients in Cohort 2. The underlying assumptions are (1) the patients for each treatment group follow a binomial distribution separately in each Cohort except Cohort 1, which will be combined with Cohort 2, (2) patients for each treatment group, follow the same binomial distribution in Cohorts 1 and 2.

FAS will be used.

Wilson uncorrected method:

Let

a = # responders in cipargamin arm

c = # non-responders in cipargamin arm

m = sample size of the cipargamin regimen ($a+c$)

b = # responder in the artesunate arm

d = # non-responders in the artesunate arm

n = sample size of the artesunate regimen ($b+d$)

$\theta = \pi_1 - \pi_2$ is the difference between two arms

$\hat{\theta} = a/m - b/n$ is estimated difference between two arms

Method based on the Wilson score method for the single proportion, without continuity correction:

$L = \hat{\theta} - \delta$, $U = \hat{\theta} + \varepsilon$ where

$$\delta = \sqrt{\{(a/m - l_1)^2 + (u_2 - b/n)^2\}} = z\sqrt{\{l_1(1 - l_1)/m + u_2(1 - u_2)/n\}}$$

$$\varepsilon = \sqrt{\{(u_1 - a/m)^2 + (b/n - l_2)^2\}} = z\sqrt{\{u_1(1 - u_1)/m + l_2(1 - l_2)/n\}}$$

l_1 and u_1 are the roots of $|\pi_1 - a/m| = z\sqrt{\{\pi_1(1 - \pi_1)/m\}}$, and l_2 and u_2 are the roots of $|\pi_2 - b/n| = z\sqrt{\{\pi_2(1 - \pi_2)/n\}}$.

Where z is the standard normal deviate associated with 10% level of significance (l.o.s.) two sided.

2.5.3 Handling of intercurrent events of primary estimand

The primary estimand will account for the different intercurrent events as follows:

- If a patient receives any IV rescue antimalarial medication prior to the *P. falciparum* asexual parasite assessment at 12 hours, the patient will be classified as not achieving $\geq 90\%$ reduction,
- If a patient dies prior to the *P. falciparum* asexual parasite assessment at 12 hours, the patient will be classified as not achieving 90% reduction.

Composite strategy is used to handle intercurrent events as the intercurrent events indicate that the study IV treatment is not working quickly enough to prevent clinical deterioration.

2.5.4 Handling of missing values not related to intercurrent event

All patients should be hospitalized at the time of 12 hours post treatment unless death or discontinuation from the study have occurred. Death is considered as an intercurrent events and is handled in [Section 2.5.3](#). Any missing data not related to intercurrent events will be handled according to [Table 2-1](#).

Since patients are hospitalized at 12 hours, these missing data should be rare. After receiving the IV study medication, a patient's parasite load should decrease over time such that the parasite count is lower at 12 hours than at previous visits (6 hours or earlier). That is, the probability that a patient achieves at least 90% parasite reduction is higher at 12 hours than at 6 hours. Therefore, the imputation of using parasite assessment at the latest visit prior to 12 hours is conservative. This imputation may slightly under estimate the proportion of patients with at least 90% parasite reduction at 12 hours.

Table 2-1 Handling of missing parasite data required for deriving primary endpoint

Event	Outcome
Discontinuation of study prior to parasite assessment at 12 hours, such as withdrawal of consent, COVID-19, etc.	Impute using the latest assessment prior to 12 hours including baseline. Note: the outcome is 'no' if baseline value is used.
Intermediate parasite count missing at 12 hours due to other reason (such as missing sample, technical reason, etc.)	

2.5.5 Sensitivity analyses

- After receiving antimalarial medication, a patient's parasite usually decreases log-linearly after a lag stage ([White 2011](#), [Flegg et al 2011](#)). For artemisinin derivatives, parasitaemia starts to decline in a log-linear manner almost as soon as parasitocidal drug concentrations are reached ([White 2011](#)). The Tmax is about 0.5 to 15 minutes for IV artesunate ([Artesunate PI](#)). The Tmax is about 4 hours for oral cipargamin and should be much shorter for IV cipargamin. Missing data of parasite counts at 12 hours could be well estimated using a log linear interpolation of the 2 parasite counts immediate before and after 12 hours. Since there are 3 planned parasite assessments on or after 2 hours, missing parasite count at 12 hours due to early discontinuation could be estimated using patient specific log linear regression if there are at least 2 parasite counts prior to the discontinuation. A sensitivity analysis will be performed using interpolation for missing data at intermediate time points

and extrapolation using a log linear regression if there are at least 2 parasite counts prior to discontinuation. Regression line will be fitted for each patient separately. In the event that a patient does not have at least 2 parasite counts prior to discontinuation, the patient will be imputed as not achieving $\geq 90\%$ reduction at 12 hours. Parasite counts below the limit of detection will be substituted using the limit of detection. If a patient's parasite count becomes below the limit of detection, only the first parasite count below detection will be used.

- The severity of disease is different between Cohort 1 and Cohort 2, which might impact the ability to achieve $\geq 90\%$ parasite reduction, ie., resulting in a different binomial distribution between Cohorts 1 and 2. Therefore, two-sided 90% confidence intervals (CI) for the difference between each IV cipargamin dose regimen vs IV artesunate will be provided for Cohort 1 and Cohort 2 separately, using handling of missing values not related to intercurrent events specified in [Section 2.5.4](#) and in this section.
- In order to assess the impact of IV rescue medication on parasites reduction, a listing of parasites details over time will be provided for the patients receiving IV rescue.

2.5.6 Supplementary analysis

For each Cohort (except Cohort 1, which will be pooled with Cohort 2), the difference between a cipargamin dose regimen and artesunate in the proportion of patients with $\geq 90\%$ reduction in parasite at 12 hours will be performed using the Fisher exact test.

For each cipargamin dose regimen that is selected for Cohorts 3-5, the difference versus artesunate in proportion of patients with $\geq 90\%$ reduction in parasite at 12 hours will be evaluated by pooling data from all cohorts to show if the IV cipargamin dose regimen is superior to IV artesunate. The treatment difference will be evaluated based on 2-sided 95% CIs using a Mantel-Haenszel estimate of the common risk difference stratified by cohort (Cohorts 1 and 2 will be pooled together and used as a single stratum)(SAS manual version 13.2). P-values will be provided using a Cochran-Mantel-Haenszel test (CMH) stratified by cohort.

Similarly, between treatment difference will be evaluated in children by repeating the above supplementary analysis on pooled Cohorts from 3-5 only.

A 2-sided 95% CIs for the proportion of patients with achieving primary endpoint for each treatment group will be provided based on the Clopper-Pearson exact method on pooled cohort.

These supplementary analyses target a different hypothesis to show superiority of each cipargamin dose regimen over artesunate and will be performed using the FAS and handling of intercurrent events and missing values not related to intercurrent events according to [Section 2.5.3](#) and [Section 2.5.4](#).

2.5.7 Supportive analyses

The analyses specified in [Section 2.5.2](#), [Section 2.5.5](#) and [Section 2.5.6](#), will be repeated using the PPS.

Primary endpoint will be summarized descriptively by the subgroups defined in [Section 2.2.1](#). Local lab data will be used for all primary endpoint analysis for all cohorts. All the primary endpoint analysis will also be performed using central lab data for Cohorts 1 and 2.

2.6 Analysis of the key secondary objective

2.6.1 Secondary estimand

The secondary clinical question of interest is: What is the difference between IV cipargamin and IV artesunate in clinical success at 48 hours without the need of IV rescue antimalarial medication?

The justification for the secondary estimand is that it will reflect the clinical outcome including recovery from the most severe symptoms of the disease with IV treatment before earliest possible administration of oral antimalarial medication at 48 hours. This objective is being evaluated for possible use in Phase III study.

The secondary estimand is described by the following attributes:

1. **Population:** patients with severe *P. falciparum* malaria and treated with at least one dose of IV study medication. Further details about the population are provided in Section 5 in the protocol.
2. **Variable:** A binary outcome indicating clinical success- patient is alive and has absence of asexual parasites and no critical signs of severe malaria (See [Section 2.1.1](#) for further details) at 48 hours.
3. **Treatment of interest:** IV cipargamin vs IV artesunate. Further details about cipargamin and artesunate are provided in Section 6 in the protocol.
4. **Intercurrent event:** receive IV rescue antimalarial medication before assessing the clinical success prior to H48.
5. **Summary measure:** Proportion of patients with clinical success with 90% CI within a treatment group as well as the difference between the cipargamin and artesunate treatment group.

2.6.2 Statistical hypothesis, model, and method of analysis for secondary estimand

There are no pre-specified hypotheses for secondary endpoints. Model, method of analysis, and handling of missing values/censoring/discontinuations are presented in the following subsection.

The clinical success at 48 hours will be evaluated using the FAS with data from all cohorts pooled.

Intercurrent events and other non-intercurrent events including partial missing data that may occur and affect the derivation of secondary estimand will be handled in [Section 2.6.3](#).

Two-sided 90% CIs for the difference between a cipargamin dose regimen and artesunate will be provided using a Mantel-Haenszel estimate of the common risk difference stratified by cohort where Cohorts 1 and 2 will be combined. Mantel-Haenszel estimate is a weighted risk difference with weight roughly proportional to strata size. It's an unbiased estimation of risk difference in the population under the following assumptions either (1) the risk difference is same across different strata or (2) the strata sizes in study resemble the strata size in the disease

population at large. Two-sided 90% CIs for the difference for the Mantel-Haenszel estimate of the common risk difference will be calculated using the local lab data only.

Descriptive statistics will be provided by cohort using the local lab data in addition to all cohorts pooled. Descriptive statistics will be provided for Cohorts 1 and 2 using the central lab data.

2.6.3 Handling of intercurrent events and missing data for secondary estimand

Handling of intercurrent events will be done according to [Table 2-2](#); and missing data not related to intercurrent events will be handled according to [Table 2-3](#).

Table 2-2 Handling of intercurrent events and other events that may occur and affect the derivation of secondary estimand

Event	Outcome
Receive IV antimalarial rescue medication prior to 48 hours	Not clinical success

Table 2-3 Handling of missing data that may occur and affect the derivation of secondary estimand

Reason for missing assessment	Method of imputation
Discontinue the study prior to 48 hours, such as withdrawal of consent, COVID-19, etc.	Not clinical success due to early discharge
Missing parasite assessment at 48 hours [§]	
• Not clinical success if asexual parasites present in the latest visit prior to 48 hours• Ignored* otherwise
Altered consciousness: missing Prostration, missing Glasgow Coma Score or missing Blantyre coma score in relevant age groups [§]	Use the result from the latest visit prior to 48 hours (including baseline) for each missing item
Renal impairment: missing SCr [§]	
• Not clinical success if Renal Replacement Therapy is used at 48 hours• Use the latest SCr prior to 48 hours
Acidosis and respiratory distress: missing plasma lactate or missing respiratory distress assessment [§]	Use the result from the latest visit prior to 48 hours (including baseline) for each missing item
* determination of clinical success depends on other assessments.	
[§] Partial data missing, unlikely since patients are in the hospital	

Note: partial data missing should be rare since patients are still hospitalized at 48 hours.

2.6.4 Sensitivity analysis for secondary estimand

For patients who discontinue the study prior to the H48 assessments, such as withdrawal of consent, COVID-19, etc. the worst outcome (not clinical success) is used. This may underestimate the clinical success rate at 48 hours. To assess the impact of worst assessment on the treatment difference, a sensitivity analysis will be performed by imputing missing outcome using the best outcome as "Clinical success".

2.6.5 Supplementary analysis for secondary estimand

Analysis defined for secondary estimand will be repeated by pooling all patients from Cohorts 3-5.

2.6.6 Supportive analysis for secondary estimand

Clinical success at 48 hours will be summarized descriptively by the subgroups defined in [Section 2.2.1](#).

The analyses specified in [Section 2.6.2](#) and [Section 2.6.5](#), will be repeated using the PPS. Additionally, analysis specified in Section 2.6.2 may be performed using the PPS after excluding the patients who took other antimalarial drugs (PD ID= COMD01) before assessing the clinical success at 48 hours, if in case there are enough number of such patients exists.

A 2-sided 90% CIs for the proportion of patients with clinical success for each treatment group will be provided based on the Clopper-Pearson exact method on pooled cohorts.

A 2-sided 90% CIs for treatment difference between cipargamin and artesunate will be provided by cohort using the Wilson uncorrected method.

2.7 Analysis of remaining secondary efficacy objective(s)

Other secondary endpoints will be descriptively presented and tabulated (n, mean, standard deviation, median, minimum, and maximum for continuous variables; n and percent for categorical variables) by treatment group for each cohort separately. Cohort 2 will be also evaluated together with Cohort 1. For stratified analysis, Cohort 1 will be combined with Cohort 2. The cipargamin dose regimen that is dropped after reviewing data from Cohorts 1-2 will be included only in the by-cohort analyses. For those treatment groups that are selected for Cohorts 3-5, descriptive statistics will be provided by treatment group using all pooled Cohorts (1-5) as well as separately pooled Cohorts 3-5. When data from different cohorts are pooled, an IV cipargamin regimen in Cohorts 3 to 5 (aged < 12 years) will be analyzed together with the equivalent IV cipargamin regimen as used in Cohorts 1 and 2 (aged ≥ 12 years). Such an IV cipargamin dose regimen will be denoted and labeled using the same cipargamin treatment group. Analysis will be based on FAS.

2.7.1 Secondary efficacy endpoints

Secondary efficacy endpoints include:

- Clinical success at 24 hours and 72 hours, hospital discharge Day 6, Day 8, Day 15, Day 22, and Day 29. See [Section 2.1.1](#) for definition of clinical success.
- Individual signs of severe malaria over time
 - Altered consciousness - Prostration or GCS < 11 for patients > 5 years old or BCS < 3 for patients ≤ 5 years old
 - Renal Impairment- Serum creatinine > 3 x ULN or > 3 mg/dL or need for renal replacement therapy
 - Acidosis- Plasma lactate > 4 mmol/L Or Respiratory distress – present or absent

- Severe anemia- Hb < 5 g/dl or Hb < 7g/dl in pediatric and adults respectively with parasite count of > 10,000/μl or need of blood transfusion
- Jaundice- Serum bilirubin > 3 g/dl with parasite count of > 100,000/μl
- Hypoglycemia- plasma glucose < 40 mg/dL
- Proportion of patients with convulsion developing or persisting > 6 hour after start of IV study treatment
- Proportion of patients developing any new severe malaria signs (as per WHO severe malaria criteria) after treatment
- Proportion of patients with neurological sequelae (by adjudication) at Day 29
- Time to oral antimalarial therapy (in hours)
- Time to recover from prostration (in hours) in patients who are prostrated at baseline
- Proportions of patients with $\geq 90\%$ *P. falciparum* asexual parasite reduction from baseline at 24 and 48 hours
- *P. falciparum* asexual parasite reduction ratios (PRR) at 12, 24 and 48 hours
- Time to *P. falciparum* asexual parasite clearance (PCT) (in hours)
- Time to fever clearance (FCT) (in hours)
- PCE slope half-life
- Proportion of patients with recrudescence and reinfection by Day 29

Hospital discharge day will be defined as the visit day where healthcare resource utilization has the hospital discharge date.

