All analyses described below will be performed using the FAS without imputation for missing assessments, ie., missing assessments will be excluded from analysis.

For the following individual signs of severe malaria, the shift table of post-baseline presence relative to baseline presence or not will be provided by visit (24 hours, 48 hours, 72 hours, 96 hours, at hospital discharge, Day 6, Day 8, Day 15, Day 22, and Day 29), cohort, and treatment group:

- Altered consciousness - Prostration or GCS < 11 for age > 5 yrs / BCS < 3 for age ≤ 5 years
- Renal Impairment- Serum creatinine > 3 x ULN or > 3 mg/dL or need for renal replacement therapy
- Acidosis- Serum lactate > 4 mmol/L
- Respiratory distress – present or absent
- Severe anemia- Hb < 5 g/dl or Hb < 7g/dl in pediatric and adults respectively with parasite count of > 10,000/μl or need of blood transfusion
- Jaundice- Serum bilirubin > 3 g/dl with parasite count of > 100,000/μl
- Hypoglycemia- plasma glucose < 40 mg/dL

Number and percent of participants will be provided by cohort and treatment group for the following events related to severe malaria:

- Convulsion developing or persisting > 6 hour after the IV study treatment. Note: “persisting > 6 hour” means that convulsion is present at baseline and again at a visit that is > 6 hours after IV study treatment.
- New severe malaria signs (as per WHO severe malaria criteria) after the IV study treatment
- Neurological sequelae (by adjudication) at Day 29

Neurological Examination results will be summarized descriptively by visit, cohort, and treatment group.

For the following time to event variables, the first visit with the event will be used to calculate the time if a participant experiences the event. If a participant does not experience the event, the time will be censored at the last visit assessment for specific type of event (such as last sit assessment, etc.) with the exception of date of discontinuation (or death) for time to oral antimalarial therapy.

- Time to oral antimalarial therapy (in hours),
- Time to recover prostration in participants who are prostrated at baseline

Descriptive statistics will be provided using the Kaplan-Meier method and Kaplan-Meier curves will be presented by cohort and treatment.

Day of discharge from hospital will be summarized descriptively by cohort and treatment group. Day of death will be used in case of death during hospitalization.

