Key signs of Severe Malaria are Altered consciousness, Renal impairment, Acidosis, and Respiratory distress.

Signs of severe malaria

The following signs of severe malaria will be monitored at every visit during the entire study duration.

- **Altered consciousness** – Prostration (inability to sit or drink or breast feed) or GCS < 11 for patients > 5 years / BCS < 3 for patients ≤ 5 years of age
- **Renal Impairment** - Serum creatinine > 3xULN or > 3 mg/dL or need for renal replacement therapy (RRT)
- **Acidosis** - Plasma lactate > 4 mmol/L or Respiratory distress.
Respiratory distress is defined as rapid, deep and labored breathing (costal indrawing, use of accessory muscles and nasal flaring)- present or absent.
In database, Plasma lactate is captured under lactic acid.
- **Severe anemia** - Hb < 5 g/dl or Hb < 7g/dl in pediatric and adults respectively or need of blood transfusion
- **Jaundice** - Serum bilirubin > 3 mg/dl
- **Hypoglycemia**- plasma glucose < 40 mg/dL
- **Blantyre coma scale (BCS)** is a number from 0 to 5 based on [Appendix 5, Table 5-1](#) for patients ≤ 5 years. The score is determined by adding the results from three categories: Motor response, verbal response, and eye movement. The minimum score is 0 which indicates poor results while the maximum is 5 indicating good results.

- **Glasgow Coma Scale (GCS)** is a clinical scale used to reliably measure a person's level of consciousness for age > 5 years. The score is determined by adding the results from three categories: Motor response, verbal response, and eye movement. A person's GCS score can range from 3 (completely unresponsive) to 15 (responsive) based on [Appendix 5, Table 5-2](#).

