2.7.2.2 Analyses of Individual signs of severe malaria

The following analysis for new severe malaria signs (as per WHO severe malaria criteria) after the IV study treatment will be performed.

The shift table of post-baseline presence relative to baseline presence of Individual signs of severe malaria or not will be provided by visit (24 hours, 48 hours, 72 hours, at hospital discharge, Day 6, Day 8, Day 15, Day 22, and Day 29), cohort, and treatment group. There are 7 individual signs and symptoms of malaria (See [Section 2.1.1](#)). Number and percent of patients with count of 0, 1, 2, 3, 4, 5, 6, and 7 different signs and symptoms by timepoint will be provided for each cohort and treatment group.

For BCS and GCS, individual scores for each category (eye opening, verbal response, motor system) will be listed. Refer to [Appendix 5, Section 5.1](#) for more details.

In order to assess the impact of IV rescue medication, a listing of signs and symptoms of severe malaria over time will be provided for the patients receiving IV rescue.

Analysis will be based on FAS using observed data.

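### Post-baseline severe anaemia and jaundice have two conflicting definitions; the one with a parasite count makes jaundice and the haemoglobin limb of anaemia unrecordable once parasites fall

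*SAP*

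**What the plan says.** The two signs are defined in six places, which fall into two groups.

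With a concurrent parasite count:
- SAP 2.7.1, endpoint list: "Severe anemia- Hb < 5 g/dl or Hb < 7g/dl in pediatric and adults respectively with parasite count of" > 10,000/µl, followed by "or need of blood transfusion"; and "Jaundice- Serum bilirubin > 3 g/dl with parasite count of" > 100,000/µl.
- Protocol 12.5.1, endpoint list: the same two conditions.
- Protocol 12.5.1, list behind the sign tables: the same again. For these signs "the shift table of post-baseline presence relative to baseline presence or not will be provided by visit", from 24 hours to Day 29.
- Protocol Table 16-6, the modified WHO definition used for entry: the same counts, with no transfusion alternative.

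Without a count:
- SAP 2.1.1: severe anaemia is "Hb < 5 g/dl or Hb < 7g/dl in pediatric and adults respectively or need of blood transfusion", and jaundice is "Serum bilirubin > 3 mg/dl".
- Protocol 8.3.1.2: the same, except that bilirubin is printed in g/dl.

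The cross-references do not settle it. Protocol Table 2-1 sends the individual-signs endpoint to 8.3.1.2. SAP 2.7.2.2 states "There are 7 individual signs and symptoms of malaria" and refers to 2.1.1. The same SAP section opens by describing the analysis as one of new signs by the WHO criteria, and the only WHO-based definition in the documents is Table 16-6. SAP section 4 lists no change from the protocol's analyses.

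**The concern.** A parasite count is natural in an entry definition. After treatment has started it makes the sign depend on the drug's antiparasitic action. A participant whose haemoglobin or bilirubin has not moved can shift from present to absent only because parasites fell. The table then partly repeats parasite clearance instead of showing recovery, and the arm that clears faster can look better on unchanged laboratory values.

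Two programmers could follow the documents faithfully and produce different tables. Protocol 8.3.3 relies on the individual signs for an in-depth view of efficacy. SAP Table 2-13 marks this output Yes for both the Cohort 2 interim assessment and the Cohort 4 DMC review. At that DMC review, individual signs and rescue use are the only efficacy outputs marked Yes; the rest are Optional or No. Enrolment of Cohort 5 follows that meeting (Protocol 4.4).

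**Working it through.** The plan gives no figure on this point to reproduce. The check has three parts.

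**1. What the count does by logic.** Under SAP 2.7.1 and Protocol 12.5.1:
- Jaundice has one limb: bilirubin above the cut-off and count > 100,000/µl. At or below that count it is absent at any bilirubin.
- Severe anaemia has two limbs: (low Hb and count > 10,000/µl) or need for transfusion. At or below 10,000/µl the first limb is closed. The second, on the natural reading, stays open. The and/or grouping is not bracketed.

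**2. When the limbs close on artesunate.** Inputs: mean 24-hour parasite reduction ratio R of 7 to 43 (Protocol 4.2); thresholds T of 10,000 and 100,000/µl. Assumption: log-linear decline from baseline B.

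Count at t hours = B × R^(−t/24), so the limb is still open at t only if B > T × R^(t/24).

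| Limb | Visit | R = 7 | R = 43 |
|---|---|---|---|
| Hb, T = 10,000 | 24 h | B > 70,000 | B > 430,000 |
| Hb, T = 10,000 | 48 h | B > 490,000 | B > 18,490,000 |
| Jaundice, T = 100,000 | 24 h | B > 700,000 | B > 4,300,000 |

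Hours until closure = 24 × ln(B/T) / ln(R):
- Hb limb, B = 50,000: 19.9 h (R = 7) or 10.3 h (R = 43)
- Hb limb, B = 100,000: 28.4 h or 14.7 h
- Jaundice, B = 250,000: 11.3 h or 5.8 h

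For example, a participant entering at 50,000/µl with Hb 4 g/dl, unchanged and without need for transfusion, is present at baseline and absent at 24 hours across this whole range.

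**3. Whether the arms differ.** SAP 5.8.4 expects most cipargamin participants to clear by 24 hours, from oral data in uncomplicated malaria, and a median artesunate clearance time above 40 hours. A participant cleared by 24 hours cannot meet either count at any listed visit, unless parasites later return above it.
- Jaundice: at 24 hours, the first listed visit, artesunate participants also need a baseline of at least 700,000/µl to be counted. The loss is largely the same in both arms.
- Hb limb: at 24 hours some artesunate participants can still exceed 10,000/µl. Hypothetically, let 20% of each arm have low Hb, with no cipargamin participant above 10,000/µl. If 10%, 30% or 50% of the low-Hb artesunate participants are above it, the limb counts 0.20 × 0.10 = 2%, 0.20 × 0.30 = 6% or 0.20 × 0.50 = 10% on artesunate, against 0% on cipargamin, with identical haemoglobin.

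**Unit.** 3 g/dl is 3,000 mg/dl. It is printed in Protocol 8.3.1.2, both lists in Protocol 12.5.1 and SAP 2.7.1. SAP 2.1.1 and Table 16-6 print mg/dl.

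**The case against.** The strongest reply is that the chain of references ends at the count-free definitions: Protocol Table 2-1 leads to 8.3.1.2, and SAP Table 1-1 leads to 2.7.2.2 and from there to 2.1.1, where the bilirubin unit is also right. A programmer who follows that chain produces the sound table. This stands as a reason not to treat the artefact as certain. It does not remove the conflict, because the protocol's own shift-table list carries the counts, the SAP declares no departure from it, and 2.7.2.2 also invokes the WHO criteria.

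Three stronger readings are tempting, and the documents do not support them:
- A reader might infer that both signs vanish by definition. In the sign lists the transfusion limb survives clearance, so this is true of jaundice but only of the haemoglobin limb of anaemia. Only Table 16-6 lacks the transfusion alternative.
- A reader might take the 12-hour responder rates assumed for the sample size as the share of jaundice erased in each arm. Twelve hours is not a shift-table visit, and the cipargamin assumption is redacted. Anyone entering at or below 100,000/µl is also uncountable from the start in either arm, and entry to Cohorts 2 to 5 begins at 5,000/µl.
- A reader might infer that late anaemia is hidden from the trial. SAP 2.8.2 tabulates early and delayed haemolysis, haemoglobin falls of 10% or more, haematology shifts by visit and bilirubin multiples of the ULN, all without a parasite condition.

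**Conclusion.** The conflict is real and should be resolved. Under the wording with counts, jaundice and the haemoglobin limb of severe anaemia cannot be recorded at or below the thresholds, whatever the laboratory value. The between-arm distortion is plausible for the haemoglobin limb around 24 hours. For jaundice it is largely non-differential from 24 hours on.

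The reach is limited. These are secondary endpoints with no pre-specified hypothesis (SAP 2.7.2), and the sign tables are descriptive. Neither sign enters clinical success. The primary endpoint, clinical success and the separate haemolysis and laboratory summaries are unaffected. What is exposed is the individual-signs output, including the version supplied to the interim assessment and the DMC, and the new-signs endpoint if it is read through Table 16-6.

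The baseline figures rest on log-linear decline at published mean reduction ratios; individuals will vary, and the documents give no baseline count distribution. The 2%, 6% and 10% figures are illustrations, not estimates. The logical point in part 1 of the check needs none of these assumptions.

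**What to change.** - In Protocol 12.5.1 (both lists) and SAP 2.7.1, remove the parasite-count conditions and use the SAP 2.1.1 definitions for all post-baseline sign tables, including the shift tables and the tables of number of signs.
- Keep the counts only in Table 16-6, for eligibility.
- State in SAP 2.7.1 and 2.7.2.2 which definitions the new-signs endpoint uses after baseline, since its present label leads back to Table 16-6.
- Correct bilirubin from g/dl to mg/dl in Protocol 8.3.1.2, Protocol 12.5.1 (both lists) and SAP 2.7.1.
- SAP 1.1 indicates that Cohorts 1 and 2 are complete and that the DMC has endorsed doses. Record which definition the interim output used, and rerun that table if it carried the counts.

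The cost is SAP wording, a protocol clarification at the next amendment and a check of the table programs. No new data are needed. It should be settled before the Cohort 4 DMC outputs are produced.
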